1. A dataset to the DfE containing only the personally identifying data (i.e. name, address etc.) for the CYP in the treatment and control groups, with a list of random references numbers.
2. The evaluation data set and random references numbers to ONS (no directly identifying data will be included)

Data Management Plan

Assessment and use of existing data and creating new data

We will analyse existing routinely collected police data and may produce new quantitative and qualitative data alongside the more sensitive individual level data. Ethics approvals will be obtained from the UOB where needed that will set out the usage, storage and governance of data. The research team will respect any conditions of usage set forward by the data owners and the informed consent sheets will set out how data that is collected will be used.

For interviews, when prior consent is received, all interviews will be digitally audio recorded. The recorded data will be saved on password-protected and encrypted computers of the research co-ordinator and lead for the study and will be either transcribed in-house or sent electronically to a transcription agency that complies with

the University's data protection policy and agreed security standards set by the funder. The transcripts will be stored on the computer of the research fellow in Word Format and will be thematically analysed by the study lead and research fellow.

Quantitative data will be stored anonymously. If any individual data is collected, participant names will be allocated a research ID number. A separate list detailing the participant name and research ID code will be stored in an encrypted file in research co-ordinator's laptop, separate from the rest of the project files. All UOB laptops have secure encryption which satisfies the requirements of the Data Protection Act 2018. All work involving matching using names will be on UOB encrypted machines by researchers under the PI's supervision.

All data collected will be for the specific purpose of carrying out the efficacy trial and will be GDPR compliant.

Quality assurance of data

Data collection will be designed and reviewed to ensure integrity and quality. This will be achieved by having regular project team meetings and consulting research participants on an ongoing basis. Quality assurance of data will form a standing agenda item at all team meetings.

The Project manager will have ultimate accountability and oversight for quality assurance of data; however, it will be emphasised to all team members that they have a personal responsibility to produce high quality data. In order to ensure 360-degree oversight, a selection of each lead's work will also be reviewed by the co-leads and research fellow.

Quality assurance in the merged and linked data files will be ensured via the use of clear, consistent coding that will be crosschecked by members of the research team. All provided coding will be clearly annotated so that the purpose of the code is understood by any potential user. Data will also be manually examined by more than one person, either using subsets of the data for complete examination against the original data or running frequencies of the original and newly created data, for inconsistencies and errors.

Back-up and security of data

Each study lead and research fellow will store the data on their encrypted laptop. Further data back-up will be provided by using the UOB's secure network. Backup copies of data are taken at least daily or immediately if needed.

The UOB's Information Security document can be provided upon request. The project team will be mindful of not carrying/ using devices that contain sensitive data (such as personal details of participants) in 'risky' situations e.g., all members of the project team will be made aware of the issues posed by the theft of laptops etc.

This evaluation will comply with YEF's Data Archive guidance, including the collection and long-term archiving of personal data. We have considered YEF's guidance on this and will abide by it.

Data Monitoring

A data monitoring committee (DMC) will be established, which will be independent of the study organisers, the funder and the evaluation team. The DMC will consist of two people, one of which will act as a chair.

The DMC will have unblinded access to all data and can propose the stopping of the project. The steering committee decides on the continuation of the trial and will report to the central ethics committee.

An audit is planned after six months in the trial, which will include site visits. The audit will be conducted by the DMC committee.

Stakeholders and interests

Delivery Team

The Remedi team for this project is as follows:

- Remedi Director, [name]: Project oversight.
- Restorative Mentoring Team:

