	
The SDQ and SRDS questionnaires are completed by CYP at baseline, the end of the RM and RC interventions, and 6 months after the end of the intervention as a follow-up.
 
For the SDQ CYP are asked to recall over the past 6 months, a period defined in the measure. For the SRDS, CYP are asked to recall over the past 3 months, this was a period defined for this study, in consultation with Remedi.

--	--

Protocol version history

Version	Date	Reason for revision
1.5 [latest]	30/4/2024	Updated to agree with the Statistical Analysis Plan
1.4	6/12/2023	Feedback from YEF
1.3	10/10/2023	Feedback from peer reviewer
1.2	26/7/2023	Feedback from YEF
1.1	4/7/2023	Feedback from YEF
1.0 [original]	15/5/2023	[leave blank for the original version]

Any changes to the design or methods need to be discussed with the YEF Evaluation Manager and the developer team prior to any change(s) being finalised. Describe in the table above any agreed changes made to the evaluation design. Please ensure that these changes are also reflected in the SAP (CONSORT 3b, 6b).

Table of contents

Protocol version history.....	3
Table of contents	4
Study rationale and background.....	5
Impact evaluation	28
Outcome measures.....	36
Implementation and process evaluation	42
Cost data reporting and collecting.....	44
Diversity, equity and inclusion.....	45
Ethics and registration	45
Data protection.....	46
Stakeholders and interests	49
Risks	51
Timeline.....	52
References	54
Appendix 1: Changes since the previous YEF evaluation.....	58
Appendix 2: Outcome measure questionnaires	59

Study rationale and background

Remedi have developed and are delivering a restorative mentoring programme for children and young people (CYP) to be used as a means of diversion from the criminal justice system (CJS).

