The trial will be a two-armed individually randomised controlled trial. It will include an impact and a process and implementation evaluation. Upon referral to Remedi, eligible children and young people (CYP) will be randomly assigned to receive restorative mentoring (RM, the treatment group) or restorative choices training (RC, the control group) on a 1:1 basis. The primary outcome of interest in this study will be contact with police, as perpetrators, victims or missing person episodes. The secondary outcomes will be the CYP's emotional and behavioural difficulties (as assessed by the Strengths and Difficulties Questionnaire) and their self-reported delinquency (as reported in the Self-Report Delinquency Scale (SRDS)). The process and implementation evaluation will consider the delivery of the Remedi interventions and the experience of them by all relevant groups. This design is considered by the research team to be the most appropriate to understand how the RM intervention operates and to assess its impact.

This design was used during a one-year pilot trial. No amendments have been made to the intervention or the study design as a result of this trial however the study did provide learning regarding the implementation of the study protocol which will support the current study.

The RM intervention began operation in Greater Manchester in April 2022. The RM intervention consists of 12 weeks of support comprised of three components, intensive one to one mentoring support for CYP based on 3-4 sessions per week, support for their family to address conflicts/improve communication and relationships, and restorative justice with relevant and appropriate victims of offences or incidents. All CYP in the treatment group will receive the mentoring component but the use of either of the other components will be determined by an initial needs assessment. The CYP in the control group will receive RC, a short mentoring scheme focused on the CYP understanding the causes and effects of their actions. This consists of four sessions usually lasting 1-2 hours (depending on the attention abilities of participants). The sessions take place over a period dictated by the availability of the CYP - they can all take place during a week or at most over four weeks. Both RC and RM will be delivered by Remedi.

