This is a newly developed intervention introduced in Spring 2022, as part of the pilot study undertaken by the current research team. As part of this efficacy study, the intervention will run from April 2023 until April 2025.

CYP will be referred to Remedi via the police and youth justice services on a consent-based voluntary basis. Remedi reports that these CYP frequently have low levels of awareness / understanding / empathic awareness regarding the impact of their behaviours, have problematic issues within their familial setting and face varying levels of challenges regarding

² Remedi ask for further information around these offences to understand the circumstances and whether the CYP was displaying violent behaviour when in possession.

their mental and/or emotional health. In the experience of Remedi, if unsupported these behaviours often result in greater degrees of violence/criminality³.

The RM intervention consists of three components, to provide intensive one to one support for CYP. All CYP in the intervention group will receive the mentoring component but what, if any, other component they receive will be determined by an initial needs assessment of the CYP. This takes place during an initial contact meeting between the mentor and CYP and considers the following areas of a CYP's life: relationships with parents/carers, educational attendance, mental health, self-esteem and peer pressure, emotional regulation, dealing with people in authority. The result of this assessment informs the creation of a support plan for the CYP⁴.

The three components of RM are:

i. Mentoring: This element will last for around 12 weeks, based on 3-4 1-to-1 sessions per week. The content of these sessions is determined through the creation of an 'Action Plan' agreed with the CYP with Specific, Measurable, Achievable, Relevant and Time-bound (SMART) goals and expectations established.

ii. Restorative Justice (RJ): Provision of a full RJ intervention (whether direct or indirect) with harmed individuals identified and willing to take part RJ will be offered and mentioned during the mentoring work to give many opportunities to take part – using Remedi's empathic thinking work during the mentoring. An RJ intervention will not be able take place without an identified or willing victim

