The overarching objective is to explore whether the RM intervention has greater impact than the RC intervention in terms of CYP's contact with the police and emotional and behavioural difficulties. The study has the following research questions:

1. What is the impact of the RM intervention on the contact with the police of CYP who experience it?
 - a. Is this greater than the impact of the RC intervention?
2. What is the impact of the RM intervention on the emotional and behavioural difficulties of CYP who experience it?
 - a. Is this greater than the impact of the RC intervention?
3. Does any impact vary across subgroups, including CYP demographic characteristics (age, sex and ethnicity) and the exact variant of the RM intervention received (which combination of the three elements received; mentoring, restorative-based family support, restorative justice).⁶

To achieve the overarching objective of the impact evaluation, it is necessary that:

- Regular fidelity checks are carried to ensure that the approved protocol is closely followed;
- That the blinding arrangements are in place;
- Data collection is regularly observed for timeliness and consistency;
- The necessary number of CYP recruitment is reached;
- The data are analysed according to the Statistical Analysis Plan.

YEF will not have any role in the collection or interpretation of the data, or in the decision to submit results.

We will be required to provide monitoring information to the funder quarterly on the progress of the study.

⁶ This will be examined via exploratory analyses.

Any changes to the protocol will be logged in a change log following discussion with the provider and funder.

Design

The trial will be a two-armed (RM and RC) individually randomised controlled trial. Upon referral to Remedi, CYP who have committed a violent offence or have displayed violent behaviours will be randomly assigned to RM (the treatment group) or RC (the control group) on a 1:1 basis.

Table 1: Randomized Control Trial protocol

Step 1:	CYP is referred to Remedi
Step 2:	Remedi assesses eligibility. Ineligible cases are excluded.
Step 3:	Informed consent/assent is provided by eligible CYP.
Step 4:	Data on CYP are collected (SDQ, SRDS questionnaires).
Step 5:	Randomisation done by the University of Birmingham: CYP is assigned to RM or RC.
Step 6:	CYP receives RM or RC.
Step 7:	Right after the interventions are completed, data on CYP are collected (SDQ, SRDS questionnaires) for short-term outcomes.

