Step 8:	For CYP completing the interventions in the first 18 months of the trial, follow-up SDQ and SRDS questionnaires will be collected, 6 months after the completion of the interventions.
Step 9:	One month before the trial ends, police administrative data are collected from the Police National Computer via GMP.

Table 2: Trial design

Trial design, including number of arms		Two-arm Randomised Controlled Trial
Unit of randomisation		Individual CYP
Stratification variables (if applicable)		N/A
Primary outcome	variable	The primary outcome of interest in this study will be contact with the police, as perpetrators, victims or missing person episodes.

	
measure (instrument, scale, source)
	
Police contact data will be taken from Greater Manchester Police administrative records. Police contact data is a count variable starting at 0. These data will be collected one month before the trial ends. Data will be taken for a period 1 year prior to the recruitment date. Every CYP will have a 3-month follow-up period after completion of the intervention.

Secondary outcome(s)
	
variable(s)
	
The secondary outcomes will be the CYP's emotional and behavioural difficulties and self-reported delinquency. Emotional and behavioural difficulties are measured by the following three variables:
 
 1) Internalizing score 2) Externalizing score 3) Total difficulties 
Self-reported delinquency is measured by:
 
 4) Variety of delinquency 5) Volume of delinquency
	
measure(s) (instrument, scale, source)
	
The first three scores are measured with the Strengths and Difficulties Questionnaire (SDQ). The remaining two scores (4 & 5) are measured with the Self-Reported Delinquency Scale (SRDS).
 
The SDQ and SRDS are completed by CYP at the point of consent, the end of the interventions and 6 months after the end of the interventions as a follow-up (for CYP who start the interventions in the first 18 months of the trial).
 
For the SDQ CYP are asked to recall over the past 6 months, a period defined in the measure. For the SRDS, CYP are asked to recall over the past 3 months, this was a period defined for this study, in consultation with Remedi.
 
In the pilot study 73% of CYP consented into the interventions completed the initial questionnaires,

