This part of the analysis will be exploratory as we will only have outcome measures for CYP who complete the survey at the end of the treatment. Therefore, we will obtain an estimate of the treatment's effect for those who finish the treatment. Additionally, it is important to acknowledge potential limitations in terms of statistical power since the sample size in this case will be smaller.

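### End-point SDQ and SRDS are timed to each arm's own completion, so the recall windows differ by arm: severely for SRDS, partly for SDQ

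*Protocol*

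**What the plan says.** The order of events in Protocol Table 1 is consent, baseline questionnaires, randomisation, intervention, then the end-point questionnaires: "Right after the interventions are completed, data on CYP are collected (SDQ, SRDS questionnaires) for short-term outcomes".

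The two programmes differ greatly in length. For the RC sessions, "they can all take place during a week or at most over four weeks" (Study rationale and background; repeated under Control Group). For RM, "The RM intervention consists of 12 weeks of support comprised of three components", and of the mentoring component, "This element will last for around 12 weeks, based on 3-4 1-to-1 sessions per week".

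Recall periods are the same at every time point. Table 2 states "For the SDQ CYP are asked to recall over the past 6 months, a period defined in the measure" and "For the SRDS, CYP are asked to recall over the past 3 months". Both periods are printed on the forms in Appendix 2.

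The SAP (Secondary outcome analysis) compares arm means and fits a linear regression on arm, sex, age, ethnicity, district, prior police contact and referral source. It has no baseline SDQ or SRDS score and no term for time. It calls the analysis exploratory because data come only from children and young people (CYP) who complete the end-of-treatment survey, adds that power is limited, and concludes: "Therefore, we will obtain an estimate of the treatment's effect for those who finish the treatment". Neither document mentions that the recall windows differ by arm.

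A follow-up is planned six months after the end of each intervention. Table 1, Step 8 opens it with "For CYP completing the interventions in the first 18 months of the trial". Table 2, the Secondary outcomes section, Longitudinal follow-ups and the SAP's Design overview instead refer to CYP who start or begin in that period, and the Timeline uses consent up to 31 July 2024.

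**The concern.** A questionnaire with a fixed look-back describes the period before it is filled in. RC CYP fill it in within weeks of baseline, so they largely report again on time that their baseline form already covered. RM CYP fill it in about two to three months later, and their SRDS covers almost only new time. Where the window sits is decided by arm, so no covariate in the regression can separate it from the treatment effect. Adding a baseline score would not do so either.

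A concrete case: CYP enter the trial because of violent behaviour. At zero lag, an incident between one and nine weeks before baseline falls inside every RC end-point SRDS window and outside the RM window. The event that led to referral can be counted in one arm only.

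This matters because Protocol Table 4 uses both scales to establish whether RM is more effective than RC, and the SDQ is the only quantitative source for research question 2.

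**Working it through.** **The plan's own figures.** Neither document gives a figure for the recall windows, so there is none to reproduce. The questionnaire counts do reproduce: 0.73 × 352 = 257 at baseline, 0.42 × 352 = 148 at the end point, and 0.10 to 0.20 × 352 = 35 to 70 at follow-up.

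**Inputs.**
- Window W: 13 weeks (SRDS, three months) or 26 weeks (SDQ, six months), from Table 2.
- Duration D: 1 to 4 weeks (RC) or 12 weeks (RM), from Study rationale and background.
- Lag L from baseline to first session: not stated. Taken as 0, with 4 weeks as the other end of an assumed range.

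**Share of the end-point window before baseline** = max(0, W − D − L) / W.

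| Scale | Lag (weeks) | RC, D = 1 | RC, D = 4 | RM, D = 12 |
|---|---|---|---|---|
| SRDS | 0 | 12/13 = 92% | 9/13 = 69% | 1/13 = 8% |
| SRDS | 4 | 8/13 = 62% | 5/13 = 38% | 0% |
| SDQ | 0 | 25/26 = 96% | 22/26 = 85% | 14/26 = 54% |
| SDQ | 4 | 21/26 = 81% | 18/26 = 69% | 10/26 = 38% |

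For SDQ the arms differ by 31 to 42 points at either lag.

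**What this could do to a comparison with no treatment effect.** Assume that behaviour falls by the same fraction r in both arms from baseline and that the score averages over its window. At zero lag the expected score, relative to baseline level, is 1 − r × D/W. At r = 0.30:
- SRDS volume: RM 1 − 0.30 × 12/13 = 0.723; RC 1 − 0.30 × 1/13 = 0.977 or 1 − 0.30 × 4/13 = 0.908. RM/RC = 0.74 to 0.80.
- SDQ: RM 1 − 0.30 × 12/26 = 0.862; RC 0.988 or 0.954. RM/RC = 0.87 to 0.90.

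Across r = 0.10 to 0.50 the ratio runs from 0.94 to 0.56 for SRDS volume and from 0.97 to 0.78 for SDQ. With a four-week lag and r = 0.30, SRDS gives 0.70/0.885 = 0.79 (RC one week) to 0.70/0.815 = 0.86 (RC four weeks). If behaviour rises instead, every ratio exceeds 1 and RC looks better.

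**Six-month follow-up.** At zero lag it falls at D + 26: weeks 27 to 30 in RC and week 38 in RM, a difference of 8 to 11 weeks. The SRDS windows open at weeks 14 to 17 (RC) and 25 (RM), the SDQ windows at weeks 1 to 4 (RC) and 12 (RM). No part precedes randomisation in either arm.

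**Who is compared.** Finishing RM mentoring means about 12 × 3 = 36 to 12 × 4 = 48 sessions; finishing RC means four.

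**The case against.** Several stronger readings are tempting, and the documents do not support them.

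- A reader might infer that only RC looks back mainly before baseline. That is true for SRDS. For SDQ, which supplies three of the five secondary variables, RM's window is also 54% pre-baseline at zero lag, so the imbalance is partial.
- A reader might infer that every secondary comparison is affected. The follow-up windows lie wholly after randomisation, so this mechanism is absent there.
- A reader might infer that the bias favours RM. That requires behaviour to fall after referral, and the documents give no trend. The Theory of Change says that such behaviour often escalates without support. Since both arms receive some support, this does not settle the direction either.
- The statement that RC's SRDS window is mostly pre-baseline depends on the lag. At four weeks and the longest RC schedule it is 38%, though RM's is then 0%.

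It can also be said that the SAP is open about its limits. It gives completer-only data, not just low power, as its reason for calling the analysis exploratory, and the Protocol's Compliance section plans to monitor attrition. That stands for selection. It does not cover the unequal windows, which are not disclosed anywhere.

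Finally, the SAP's own Compliance section assumes that compliance does not vary with arm, because CYP consent without knowing their allocation. If so, finishers might be comparable. But not knowing the allocation at consent cannot make finishing 36 to 48 sessions equivalent to finishing four, and equal completion rates would not mean that the same CYP finish. No completion rate by arm is given, so the size and direction of any selection are unknown.

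**Conclusion.** The concern holds for the end-point comparisons. As planned, they confound arm with the period recalled: severely for the two SRDS variables (69–92% pre-baseline in RC against 8% in RM at zero lag; 38–62% against 0% at four weeks) and partly for the three SDQ variables (85–96% against 54%; 69–81% against 38%). The planned model cannot remove this. The size and sign of the resulting bias depend on the change in behaviour after referral, which the documents do not give, so the ratios above are illustrations and not estimates.

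The follow-up is free of pre-randomisation recall, but RM is assessed 8 to 11 weeks later after randomisation than RC, and response selection remains.

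Separately, the SAP is wrong to describe a contrast between respondents who finished two very different programmes as the treatment's effect in finishers. The primary outcome comes from police records and is not touched by this point.

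**What to change.** 1. Set the end-point SDQ and SRDS at one common time from randomisation in both arms, about 12 to 13 weeks, and the follow-up six months after that date. Seek both from every randomised CYP, finished or not. At 13 weeks the SRDS window would hold no pre-randomisation time, and the SDQ window would be 13/26 = 50% pre-randomisation, equally in both arms.
2. For RC CYP already assessed in weeks 1 to 4, report end-point scores within arm only, or state that the between-arm contrast is confounded by timing. Use the follow-up as the between-arm comparison, acknowledging that only 35 to 70 forms are expected.
3. Replace the SAP sentence about those who finish with a statement that the result compares respondents and is not a treatment effect in finishers. Report response by arm.
4. Reconcile the follow-up eligibility wordings to the single consent-date rule already in the Timeline.

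The timetable allows this. Last consent on 30 November 2024 plus 12 to 13 weeks is 22 February to 1 March 2025, when RM delivery ends and before the 31 March data-sharing date. Consent by 31 July 2024 plus 12 to 13 weeks plus six months is late April 2025, before follow-up closes in May. Both sums treat randomisation as following consent promptly; the interval is not stated.

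The cost is an amendment and re-contact of RC CYP some 8 to 11 weeks after their last session. The Protocol itself expects a break in contact to lower completion. RC response may drop while RM CYP are still being seen, which could make non-response unequal by arm. If RM starts late, a 12 to 13 week assessment would also come before some RM CYP finish. Items 3 and 4 need only text changes.
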